### **2.3.2 *Safety population***

The safety population is defined as randomized patients who actually received at least 1 dose or part of a dose of the IMP (injection or capsule). Patients will be analyzed according to the treatment actually received (ie, as-treated treatment group, alirocumab or ezetimibe).

In addition:

- Randomized patients for whom it is unclear whether they took the IMP will be included in the safety population as randomized.

For patients receiving double-blind IMP from both treatments during the trial, the treatment group used for as-treated analysis will be the one to which the patient was treated with the highest number of injections except in the case where the patient is randomized in the alirocumab group but received more placebo injections than alirocumab injections and took more placebo capsules than ezetimibe capsules. In that case the as-treated group is defined as alirocumab (see [Appendix D](#)). In case of the same number of injections of each treatment is received, the as-treated treatment group will be the as-randomized group.

### **2.3.3 *Anti-alirocumab antibody population***

The anti-alirocumab antibody analysis will be performed on all randomized and treated patients (safety population) with a blood sample on Week 0 (baseline) and at least one evaluable blood sample for antibodies after the first double-blind IMP injection.

### **2.3.4 Pharmacokinetic population**

The PK analysis will be performed on all randomized and treated patients (safety population) with at least 1 evaluable PK sample post first double-blind IMP injection.

## **2.4 STATISTICAL METHODS**

### **2.4.1 Demographics and baseline characteristics**

Parameters described in [Section 2.1.1](#) will be summarized by treatment group and overall treatment groups using descriptive statistics.

Continuous data will be summarized using the number of available data, mean, standard deviation (SD), median, minimum, and maximum for each treatment group. First quartile (Q1) and third quartile (Q3) will be provided for baseline lipid and HbA1c. Categorical and ordinal data will be summarized using the number and percentage of patients in each treatment group.

Parameters will be summarized on the randomized population analyzed in the treatment group to which they were randomized. Similar analyses will be done on the ITT population in the as-randomized treatment group (respectively safety population in the as-treated treatment group) and will be included in the appendices if the size of the ITT population (respectively safety population) is different (>10%) from the size of the randomized population for any treatment group. In the randomized population, parameters will also be summarized within each randomization stratum as per IVRS.

All reported patient's medical and surgical history will be presented by primary SOC and HLT. The tables will be sorted by SOC internationally agreed order and decreasing frequency of HLT based on the overall incidence across treatment groups. In addition all medical history of specific interest (see [Section 2.1.1](#)) will be presented by treatment group.

For the patients with a primary CVD prevention status, the number (%) of patients with the following comorbidities/risk factors will be tabulated:

- Diabetes mellitus with target organ damage (renal damage [microalbuminuria, or macroalbuminuria, moderate chronic kidney disease (CKD)] and/or retinopathy [pre-proliferative or proliferative diabetic retinopathy and/or laser treatment for diabetic retinopathy]);

Diabetes mellitus with 2 or more risk factors (see [Section 2.1.1](#));

- Family history of premature CHD;
- Hypertension;
- Moderate CKD.

In addition, smoking status will be summarized in patients with primary CVD prevention status.

For the patients with a secondary prevention status, the CVD history will be described using the number (%) of patients with:

History of CHD (see [Section 2.1.1](#));

- History of ischemic stroke;
- History of PAD with severity criteria:
  - Intermittent claudication and ankle brachial index  $\leq 0.90$ ;
  - Peripheral revascularization procedure (angioplasty, stenting) for PAD;
  - Thrombolysis for PAD;
  - Peripheral revascularization surgery (arterial bypass) for PAD;
  - Critical limb ischemia.

Besides:

- The number (%) of patients with a secondary prevention status with 1 or more associated comorbidity among hypertension, diabetes mellitus, moderate CKD will be tabulated.
- The number (%) of patients with history of CHD and 1 or more associated comorbidity among hypertension, diabetes mellitus, moderate CKD and/or other CVD (ischemic stroke, PAD) will be presented.

#### **2.4.2 Prior or concomitant medications**

The prior and concomitant medications will be presented for the randomized population.

Medications will be summarized by treatment group according to the WHO-DD dictionary, considering the first digit of the anatomic therapeutic category (ATC) class (anatomic category) and the first 3 digits of the ATC class (therapeutic category). All ATC codes corresponding to a medication will be summarized, and patients will be counted once in each ATC category (anatomic or therapeutic) linked to the medication. Therefore patients may be counted several times for the same medication.

The table for prior medications will be sorted by decreasing frequency of ATC followed by all other therapeutic classes based on the overall incidence across treatment groups. In case of equal frequency regarding ATCs (anatomic or therapeutic categories), alphabetical order will be used.

The tables for concomitant and post-treatment medications will be sorted by decreasing frequency of ATC followed by all other therapeutic classes based on the incidence in the alirocumab group. In case of equal frequency regarding ATCs, alphabetical order will be used.

In addition, concomitant LMTs and CV medications will be summarized by pre-specified categories/chemical class and standardized medication name.

Lipid modifying therapy (statins and other LMTs) use after randomization will be summarized over time graphically by treatment group and LMTs intensity at randomization using the following categories:

- Atorvastatin 40 to 80 mg daily or rosuvastatin 20 to 40 mg daily;

- Atorvastatin below 40 mg daily or rosuvastatin below 20 mg daily or simvastatin at any daily dose;
- LMT other than statin only;
- No LMT.

The LMTs intensity at randomization is defined as:

- High intensity is atorvastatin 40 to 80 mg daily or rosuvastatin 20 to 40 mg daily;
- Low intensity is atorvastatin below 40 mg daily or rosuvastatin below 20 mg daily or simvastatin at any daily dose.

### **2.4.3 Extent of investigational medicinal product exposure and compliance**

The extent of IMP exposure and compliance will be assessed and summarized by actual treatment within the safety population ([Section 2.3.2](#)).

#### ***2.4.3.1 Extent of investigational medicinal product exposure***

##### ***Injection (alirocumab or placebo)***

The extent of IMP exposure will be assessed by the duration of IMP exposure, and actual dose information.

Double-blinded IMP injections are those administered from randomization to completion or discontinuation of the study treatment. These injections contain:

- Placebo for patients randomized in the ezetimibe group;
- 75 or 150mg of alirocumab for patients randomized in the alirocumab group.

Total exposure will be assessed using descriptive statistics for:

- Duration of IMP injection exposure in weeks is defined as: (last dose of double-blind IMP injection date – first dose of double-blind IMP injection date + 14 days)/7, regardless of unplanned intermittent discontinuations (see [Section 2.5.3](#) for calculation in case of missing or incomplete data). Non-integer values will be rounded to 1 decimal place;
- The total number of injections by patient.

These parameters will be also analyzed per dose of alirocumab using similar definitions.

##### ***Titration***

The number and percentage of patients with an up-titration in the alirocumab group will be described. Patients with an up-titration are defined as up-titrated patients according to IVRS/IWRS Week 12 transaction with at least 1 injection of alirocumab 150 mg afterwards.

### ***Capsule (ezetimibe or placebo)***

The total exposure of capsule will be assessed by duration in weeks defined as: (last capsule intake date – first capsule intake date + 1 day) / 7, regardless of intermittent discontinuations. Non-integer values will be rounded to 1 decimal place.

All quantitative parameters above will be summarized using number, mean, SD, median, minimum, and maximum. In addition, the durations of treatment exposure will be summarized and presented graphically using bar chart displaying the percentage of patients according to the following categories:  $\geq 1$  and  $< 4$  weeks,  $\geq 4$  weeks and  $< 8$  weeks,  $\geq 8$  weeks and  $< 12$  weeks,  $\geq 12$  weeks and  $< 16$  weeks,  $\geq 16$  weeks and  $< 22$  weeks, and  $\geq 22$  weeks.

#### **2.4.3.2 Compliance**

A given administration will be considered noncompliant if the patient did not take the planned dose of treatment as required by the protocol. No imputation will be made for patients with missing or incomplete data.

Compliance will be assessed using the following parameters:

**Mean injection frequency** of IMP double-blind injections, is defined as the average number of days between 2 consecutive injections, that is: (last injection date – first injection date) / (number of injections – 1) for patients receiving at least 2 injections.

The **overall compliance** for injections will be defined for each patient as:  $100 - (\% \text{ days with under-planned dosing} + \% \text{ days with above-planned dosing})$ . Under-planned and above-planned dosing will be defined as follows, considering that injections should be performed every 2 weeks ( $\pm 3$  days as per protocol):

**Above-planned dosing percentage** will be defined for each patient as the number of days with more than 1 injection administered within the 11 days before divided by the duration of IMP injection exposure in days. For example if a patient takes a dose 9 days after his/her previous injection, then 2 days are counted as days above-planned dose.

**Under-planned dosing percentage** will be defined for each patient as the number of days with no injection administered within the previous 17 days divided by the duration of IMP injection exposure in days. For example if a patient takes a dose 18 days after his/her previous injection, then 1 day is counted as a day under-planned dosing.

These parameters will be summarized descriptively (number, mean, SD, median, minimum, and maximum).

The percentage of patients whose compliance is  $< 80\%$  will be summarized, as well as numbers and percentages of patients with 0%,  $> 0$  to  $\leq 5\%$ ,  $> 5$  to  $\leq 10\%$ ,  $> 10$  to  $\leq 20\%$ , and  $> 20\%$  day with above-planned dosing and numbers and percentages of patients with 0%,  $> 0$  to  $\leq 5\%$ ,  $> 5$  to  $\leq 10\%$ ,  $> 10$  to  $\leq 20\%$ , and  $> 20\%$  day with under-planned dosing.

According to protocol, cases of overdose are reported in the AE e-CRF pages and will be described in AE analysis (see [Section 2.1.4.1](#) and [Section 2.4.5.1](#)).

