8.8.1 Treatment accountability and compliance

IMP administration data will be recorded by the patients onto a patient's diary.

Measures taken to ensure and document IMP compliance and accountability are described below:

- The Investigator or designee will obtain via IVRS/IWRS the treatment kit numbers and he/she will dispense the treatment kits to the patient.
- The accountability is to be performed at alirocumab IMP kit re-supply visits only (see [Section 10.1.2](#)). The used and unused IMP kit(s) should be brought back to such visits for accountability purposes. Sharps container will be supplied to each patient for used auto injectors. The patients should return it to the site for destruction purpose at the end of study participation.
- All ezetimibe kits are returned by the patient at the designated visit.
- The Investigator or designee will complete the corresponding treatment log form from patient's diary.
- The Investigator/study coordinator will enter data in the appropriate e-CRF pages, according to data recorded in the treatment log form.
- The monitor will check the data consistency between e-CRF pages, treatment log forms using patient's diary, and returned unused auto-injectors or capsules of a corresponding kit.

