11.4.1.2 Compliance

Compliance will be assessed using the following parameters:

- The mean injection frequency of IMP double-blind injections will be defined for each patient as the average number of days between 2 injections, that is: (last dose date – first dose date)/(number of injections -1).

- The compliance for capsules will be defined as the number of capsules taken / (last capsule intake date – first capsule intake date + 1) * 100 during the capsule exposure period.

These parameters will be summarized descriptively (N, Mean, SD, Median, Min and Max).

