## **1.5 MODIFICATIONS TO THE STATISTICAL SECTION OF THE PROTOCOL**

There are no major changes to the protocol statistical section.

The first patient was screened on 27 July 2016(screen-failed). The first patient was randomized on 11 August 2016. There are no planned interim analyses.

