### **2.3.1.2 *Modified intent-to-treat population***

The modified intent-to-treat population is defined as all randomized patients who took at least 1 dose or part of a dose of the double-blind IMP injection and had an evaluable primary efficacy endpoint during the efficacy treatment period. The primary efficacy endpoint is evaluable when the following 2 conditions are met:

- Availability of a baseline calculated LDL-C value;
- Availability of at least 1 calculated LDL-C value during the efficacy treatment period within one of the analysis windows up to Week 24.

The efficacy treatment period is defined as the time period from the first double-blind IMP (capsule or injection, whichever comes first) up to the day of last injection +21 days or the day of last capsule intake date +3 days, whichever comes first.

Patients in the mITT population will be analyzed according to the treatment group allocated by randomization (ie, as-randomized treatment group).

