### ***Handling of computation of treatment duration and compliance if investigational medicinal product end of treatment date is missing***

If the last or first injection date (capsule administration respectively) is missing, the injection (capsule respectively) exposure duration and compliance will be left as missing.

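### Does the lack of a capsule compliance measure in SAP 2.4.3.2 hide how well the ezetimibe comparator was taken?

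*SAP*

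**What the plan says.** Protocol 11.4.1.2 lists mean injection frequency and then a capsule percentage: "The compliance for capsules will be defined as the number of capsules taken", divided by the days from first to last capsule inclusive and multiplied by 100. Both are to be summarized with N, mean, SD, median, minimum and maximum. Protocol 11.4.1 sets the population (safety) and the grouping (treatment received).

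SAP 2.4.3.2 opens with a general statement about noncompliant administrations. It then defines mean injection frequency, overall injection compliance, and above- and under-planned dosing, all tied to the injection schedule: "Under-planned and above-planned dosing will be defined as follows, considering that injections should be performed every 2 weeks". No capsule parameter follows.

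The SAP's capsule summary is exposure duration in 2.4.3.1, from first to last intake, "regardless of intermittent discontinuations". The same section says that the double-blind injections contain "Placebo for patients randomized in the ezetimibe group".

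SAP 2.5.3 still covers capsule compliance: if a first or last date is missing, "the injection (capsule respectively) exposure duration and compliance will be left as missing". SAP 1.5 states: "There are no major changes to the protocol statistical section".

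**The concern.** The trial is double-dummy. In the ezetimibe arm the daily capsule is the only randomized active drug. Under SAP 2.4.3.2 alone, the compliance figures, including the category below 80%, describe active drug in one arm and placebo in the other. Missed capsules between first and last intake would leave no trace in the SAP's compliance or exposure summaries. A reader of a superiority result over ezetimibe would want to know whether ezetimibe was taken.

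The question seems sharper for the on-treatment endpoints. They make up 5 of the 21 key secondary endpoints, including the first in the hierarchy. Their treatment period ends at the last injection + 21 days "or the day of last capsule intake date +3 days, whichever comes first", so it reacts to the last capsule but not to gaps before it. The SAP also has a missing-date rule for a variable it does not define, and SAP 1.5 does not mention the omission.

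**Working it through.** The plan states no figure on this point, so the check applies the formulas to a hypothetical ezetimibe patient.

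**Inputs.** Twelve placebo injections on schedule, Weeks 0 to 22, on Days 1, 15, …, 155 (Protocol 6.1). First capsule Day 1, last capsule Day 168, the day before the Week 24 visit on Day 169 (Protocol 8.1.2 and 1.2). The capsule counts are assumptions chosen to show the range.

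**SAP outputs, which do not use the capsule count:**

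- Injection exposure: (155 − 1 + 14)/7 = 24.0 weeks.
- Mean injection interval: (155 − 1)/(12 − 1) = 154/11 = 14.0 days.
- Injection compliance: every gap is 14 days, inside the 11 to 17 day limits, so 100 − (0 + 0) = 100%.
- Capsule exposure: (168 − 1 + 1)/7 = 24.0 weeks.
- End of efficacy treatment period: min(155 + 21, 168 + 3) = min(176, 171) = Day 171.

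**Protocol capsule compliance, taken/(168 − 1 + 1) × 100:**

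| Capsules taken | Protocol measure | SAP outputs |
|---|---|---|
| 168 | 100% | as above |
| 134 | 79.8% | unchanged |
| 84 | 50% | unchanged |
| 42 | 25% | unchanged |

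**Permanent stopping does show.** If the last capsule is on Day 84, capsule exposure is 84/7 = 12.0 weeks and the efficacy treatment period ends at min(176, 87) = Day 87.

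**Which of these outputs come from the SAP alone?** Protocol 11.4.1.1 also measures capsule exposure from first to last intake without deducting interruptions. Protocol 11.3.1.2 has the same efficacy treatment period, and Protocol 11.4.1.2 the same mean injection frequency. The SAP adds the injection compliance percentages and leaves out one item, the capsule percentage.

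**Can that item be produced as the plan stands?**

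- Formula and summary statistics: Protocol 11.4.1.2.
- Population and grouping: Protocol 11.4.1.
- Missing first or last date: SAP 2.5.3.
- Data: under Protocol 8.8.1, diary entries go through the treatment log to the e-CRF, and monitors check them against "returned unused auto-injectors or capsules of a corresponding kit". SAP Appendix D compares numbers of placebo and ezetimibe capsules taken, so it already relies on capsule counts.

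Nothing is left to the analyst's discretion.

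**The case for a change.** The strongest case for acting is that the SAP is the document programmers work from, so a measure missing there may be missing from the report. Adding it would cost one definition and one table. No reason for dropping it is given, and the surviving missing-date rule suggests an oversight. The other routes by which missed capsules could surface are partial. SAP 2.2 tabulates major and critical deviations by treatment group, but the documents do not say which capsule misses qualify. Protocol 10.3.1 has interruptions recorded in the e-CRF, including single capsules, but only those decided by the investigator.

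Much of this stands: the SAP text is incomplete, and those routes do not replace a compliance summary by arm. Three parts do not stand. First, the surviving rule in SAP 2.5.3 points to a drafting slip in a measure still intended, not to a decision to abandon it. Second, SAP 1.5 speaks only of major changes, and an omitted descriptive summary does not contradict that. Third, the insensitivity of the on-treatment period to intermittent gaps is the protocol's own rule, which a capsule table would leave as it is. Converting missed capsules into lost LDL-C points would need a dose-response assumption that the documents do not supply, so no such size is given here.

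**Conclusion.** The discrepancy between protocol and SAP is genuine but clerical, and no change to the plan is called for. The primary analysis uses all LDL-C values regardless of adherence. Capsule compliance enters no model, test, power calculation, analysis population or on-treatment period. What is at issue is one descriptive table, fully specified in the protocol and computable from data already collected. Because the formula was fixed in advance, producing it involves no post hoc choice.

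This rests on two assumptions: that the protocol's specification continues to apply where the SAP is silent, and that capsule counts are recorded as Protocol 8.8.1 describes. The 100% to 25% range shows how the formula behaves for an invented patient and is not a forecast of adherence. If the table were left out of the report, readers would lose useful context on comparator intake, but the results and their error control would be the same.

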8.1.2 Timing of administration

A training injection is planned on Week -1 (V2) with a placebo for alirocumab. A second training injection with placebo for alirocumab may be administered between Week -1 and randomization visit.

During the double-blind treatment period, alirocumab or placebo for alirocumab will be administered SC Q2W, starting at Week 0 continuing up to the last injection (Week 22) 2 weeks before the end of the DBTP. If the injection is scheduled to take place on the same date as the site visit, then the IMP should be administered after the blood sampling has been completed.

Further training with the scheduled double-blind alirocumab IMP can be done between W 0 and W 4 and at additional scheduled or unscheduled visits, as per investigator's judgment.

Double-blind IMP will start as soon as possible after the call for randomization using the treatment kit number provided by the IVRS/IWRS. The first injection after randomization will be done at the site by the patient or another designated person (such as spouse, relative, etc) under direct site staff supervision. Patients will be monitored at the investigational site for at least 30 minutes after this first double-blind injection.

Alirocumab IMP injection should be administered Q2W SC at approximately the same time of the day; however it is acceptable to have a window period of ± 3 days. The time of the day is based on patient's preference.

If by mistake or due to other circumstances an injection is delayed by more than 7 days or completely missed, then the patient should return to the original schedule of study treatment administration without administering delayed injections. On the other hand, if the delay is less than or equal to 7 days from the missed date, then the patient should administer the delayed injection and then resume the original schedule of study treatment administration.

Ezetimibe 10 mg or placebo for ezetimibe capsules will be taken orally once daily at approximately the same time of the day, with or without food. Preferably, on the injection days the IMP capsule will be administered roughly at the time of injection (either before or shortly after). The capsules must be taken until the day before the end-of-treatment visit (early or not), and not stopped at the time of the last injection.

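### The injection-compliance formula scores gaps between injections rather than adherence to the schedule, so a late dose handled as the protocol directs is charged twice and in-window dosing can lose points

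*SAP*

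**What the plan says.** SAP 2.4.3.2 opens with a protocol-based standard: "A given administration will be considered noncompliant if the patient did not take the planned dose of treatment as required by the protocol". The calculation that follows works on intervals, "considering that injections should be performed every 2 weeks" with a tolerance of ±3 days.

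- Above-planned days: "the number of days with more than 1 injection administered within the 11 days before". The worked example is that "if a patient takes a dose 9 days after his/her previous injection, then 2 days are counted as days above-planned dose".
- Under-planned days: "the number of days with no injection administered within the previous 17 days". Here the worked example charges 1 day for an 18-day gap.
- Overall compliance is 100 minus the sum of the two percentages. Each is taken over the duration of injection exposure, which SAP 2.4.3.1 defines as last minus first injection date plus 14 days.
- The SAP reports the percentage of patients below 80%, together with category tables for each component.

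Protocol 8.1.2 allows ±3 days around each fortnightly injection. If an injection is up to 7 days late, "then the patient should administer the delayed injection and then resume the original schedule of study treatment administration". If the delay is longer, the injection is skipped and the patient returns to the original schedule. Protocol 11.4.1.2 lists only mean injection frequency for injections; the overall compliance formula appears only in the SAP.

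**The concern.** The standard and the formula do not match. The protocol anchors each injection to a scheduled date, whereas the formula anchors it to the previous injection. A patient who is 4 to 7 days late and then does what Protocol 8.1.2 asks has one long gap followed by one short gap, and both are charged. The above-planned charge is triggered by an injection given on its scheduled date. The ±3-day window is likewise applied to gaps, so two injections that are each inside their window (one 3 days late, the next 3 days early) are 8 days apart and are charged.

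What is at stake is whether the compliance tables can be read at face value. Patients appear in the above-planned categories without having received an extra injection, and the below-80% flag need not follow the amount of drug received.

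**Working it through.** **Inputs.** There are 12 planned injections at Weeks 0, 2, ..., 22 (Protocol 8.1.2), so last minus first is 154 days and exposure is 154 + 14 = 168 days (SAP 2.4.3.1). For each gap g between consecutive injections, under-planned days = max(0, g − 17) and above-planned days = max(0, 11 − g). The flag needs more than 0.20 × 168 = 33.6 charged days. The original schedule is taken as running from the first injection.

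**Check against the SAP's examples.** g = 9 gives 11 − 9 = 2 above-planned days; g = 18 gives 18 − 17 = 1 under-planned day. Both agree. A perfect schedule scores 100%.

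**One late injection, next one on schedule.** A delay of d days (d up to 7) gives gaps of 14 + d and 14 − d, charged (d − 3) twice once d exceeds 3.
- d = 3: 0 days.
- d = 4: 1 + 1 = 2 days.
- d = 7: gaps of 21 and 7, so 4 + 4 = 8 days; 8/168 = 4.8%, of which 4/168 = 2.4% is above-planned.

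A late final injection is charged on the under-planned side only, because no gap follows it.

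**All 12 injections inside ±3 days.** First injection on day 0, then alternately 3 days late and 3 days early, ending late. The gaps are 17, then 8 and 20 alternating, five of each. Charge: 5 × 3 + 5 × 3 = 30 days over 154 + 3 + 14 = 171 days. Compliance = 100 − 17.5 = 82.5%.

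**All 12 taken, some non-adjacent injections late, the rest exactly on schedule.**
- Four 7-day delays: 32/168, 81.0%, not flagged.
- Five 7-day delays: 40/168, 76.2%, flagged.
- Five 6-day delays: 5 × 6 = 30/168, 82.1%, not flagged.
- In general, five delays totalling D days are charged 2(D − 15), which exceeds 33.6 only when D is at least 32.

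If the other injections use the ±3-day window in the least favourable way, a single 7-day delay can be enough: 38/165, 77.0%.

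**Three of 12 missed, the rest on schedule.**

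| Pattern | Charged / exposure days | Compliance | Below 80%? |
|---|---|---|---|
| Three isolated interior misses (28-day gaps) | 3 × 11 = 33/168 | 80.4% | No |
| Interior consecutive pair plus an isolated miss | 25 + 11 = 36/168 | 78.6% | Yes |
| Three consecutive interior misses (56-day gap) | 39/168 | 76.8% | Yes |
| Last three (Weeks 18, 20, 22) | 0/126 | 100.0% | No |

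Of the 165 ways to miss three of injections 2 to 12, 64 are flagged and 101 are not.

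**The case against.** The case for leaving the section alone has four parts.

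1. *The interval basis is stated openly.* The SAP gives worked examples, and the catch-up instruction manages an injection already outside its window, so charging the lateness is fair. That stands for the long gap. Charging a 28-day gap 11 days rather than 14 also follows from applying the 3-day tolerance consistently. It does not explain the second charge, which falls on an injection given on its scheduled date.
2. *The reversals need unusual patterns.* This stands. With other doses on schedule, a 12-of-12 patient is flagged only after about five alternate injections roughly a week late. The unflagged 9-of-12 patient escapes by 0.4 points and only if interior misses are isolated, or if the final injection is among those missed. Nothing in the documents says how often such patterns occur.
3. *Other summaries separate the patients.* Total injections (12 versus 9) and mean injection frequency (154/11 = 14.0 versus 154/8 = 19.25 days) are both reported. This offsets the problem in part; the below-80% flag is still wrong for those patients.
4. *Nothing inferential depends on it.* This stands. A reader might infer that the compliance tables underpin the on-treatment estimand. The documents do not say so: that estimand rests on the mITT population and an efficacy treatment period fixed by the first and last IMP dates (SAP 2.3.1.2). The formula also applies equally to placebo injections in the ezetimibe arm, so no bias between arms is shown.

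A reader might also take above-planned days to mean overdose. Protocol 10.4.5 defines overdose as two or more injections in fewer than 7 calendar days, which a 7-day gap does not meet, and SAP 2.4.3.2 sends overdose to the adverse event pages.

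**Conclusion.** The mismatch is real and minor. Catch-up injections 4 to 7 days late that are followed by an on-schedule injection are charged on both sides, up to 8 days (4.8%) each. Dosing wholly inside the ±3-day window can score 82.5%. The below-80% flag can misorder patients (76.2% for 12 of 12 against 80.4% for 9 of 12), but only under the conditions shown. It would be wrong to conclude that patients who miss three injections generally escape the flag: three interior misses that include a consecutive pair, or are all consecutive, are caught.

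The effect is confined to descriptive compliance tables; no analysis population or efficacy model changes. The figures assume a schedule counted from the first injection, a full course to Week 22 unless stated, and no exemption for catch-up doses, since the SAP gives none.

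**What to change.** Reconcile SAP 2.4.3.2 with Protocol 8.1.2 by changing the scoring only; no dosing rule changes.

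- Score each injection against its scheduled date with the ±3-day window. An injection inside the window scores no above-planned or under-planned days, so early in-window injections and the on-schedule injection after a catch-up score zero. The 82.5% example becomes 100%.
- Keep counting the days beyond +3 for a late injection as under-planned, once. A 7-day delay then scores 4 days, and five score 20/168, giving 88.1%.
- State how injections are matched to scheduled dates and how a missed injection is charged. If a miss keeps its present 11 days, three isolated misses stay at 80.4%, now correctly below the 88.1%.
- Beside the below-80% flag, show the percentage of scheduled injections received. The denominator should be injections scheduled up to Week 22 or permanent treatment discontinuation, so that stopping treatment is not counted as noncompliance. The two example patients would show 100% and 75%.

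Two simpler rules should be avoided. Calling days above-planned whenever injections received exceed injections due would penalise permitted early dosing: injections 2 to 12 each 3 days early would score 11 × 3 = 33 of 165 days (20%). Exempting catch-up injections altogether would hide lateness.

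The cost is SAP wording and programming from injection dates already collected. One small downside is that the figures will not match other studies using the present formula unless both are shown.
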